2.2 Targeted Therapies in MRCC

Advances in the understanding of the genetic mutation or silencing of the tumor suppressor gene, known as the von Hippel-Lindau (VHL) gene, have shown that this abnormal gene produces a deviant protein which causes the accumulation of hypoxia inducible factors (HIF), which in turn induce the production of products which are critical to the proliferation of clear-cell RCC. Three of these products are vascular endothelial growth factor (VEGF), platelet derived growth factor (PDGF), and transforming growth factor-alpha (TGF- α). All four of these cellular products, i.e., HIF, VEGF, PDGF and TGF- α , have constituted rational targets of novel therapies.

Pazopanib is a multi-tyrosine kinase inhibitor that selectively inhibits protein tyrosine kinase receptors including VEGFR1-3, PDGFR α/β , c-Kit, and Flt-3. Pazopanib demonstrated substantial anti-tumor activity in a phase II trial in mRCC with randomized discontinuation design (Hutson et al, 2009). A randomized phase III trial comparing pazopanib to placebo, either as first-line therapy in treatment-naïve patients, or after failure of one cytokine in 435 patients with advanced clear-cell RCC showed significant prolongation of median PFS in favor of pazopanib (9.2 months vs. 4.2 months for all patients, $p < 0.0000001$; 11.1 months vs. 2.8 months for treatment-naïve patients, $p < 0.0000001$; 7.4 months vs. 4.2 months for cytokine-pretreated patients).

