2.3 Rationale

In the past few years, considerable progress has been made in the management of patients with metastatic renal cell carcinoma (RCC). There are now six (five in the first-line setting) FDA-approved treatments for metastatic RCC, however most patients experience disease progression within a year or less. The vast majority of metastatic RCC patients who were enrolled on phase 3 trials with anti-VEGF therapies, sorafenib, sunitinib, pazopanib and bevacizumab plus interferon alfa had good- or intermediate-risk disease. Temsirolimus is the standard of care for the treatment of patients with advanced poor-risk RCC, based on results from a phase 3 trial comparing single-agent temsirolimus versus single-agent interferon alfa versus the combination of temsirolimus and interferon alfa. The response rate of temsirolimus in this study was 8.4 %, and the median PFS and median OS were 3.8 months and 10.9 months, respectively. There is no data on the efficacy of multityrosine kinase inhibitors (TKI) in this disease state. Therefore, it is important to investigate agents with the oral convenience and tolerability of TKIs, such as pazopanib, in advanced poor-risk RCC.

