13.0 STATISTICAL CONSIDERATIONS

This is a randomized, two-arm, parallel group, phase II trial enrolling advanced, poor-risk, clear-cell RCC. Patients will be fairly randomized to either temsirolimus (control arm) or pazopanib (experimental arm).

The maximum sample size to be accrued is 90 patients (45 in each treatment arm). The primary measure of efficacy and primary endpoint is progression free survival (PFS). PFS will be monitored on an interim basis and we will use stopping rules for futility to serve as guidelines for early termination. The stopping rules are ad-hoc in nature but are selected in a manner such that the overall type 1 error is controlled at a one-sided 10% with 80% power.

Descriptive and inferential statistics will be used to summarize treatment effects. The mean, standard deviation, median, 25% percentile, 75% percentile, minimum, and maximum will be reported for continuous variables. For discrete variables, descriptive analyses will be based on the distribution of discrete outcomes and will be reported as percentages and patient counts. Time to event endpoints will be descriptively summarized by Kaplan-Meier curves. Point and interval estimates of treatment effect will be based on maximum likelihood methods. For binomially distributed variables, we will report differences in proportions between treatment groups and the 95% confidence interval associated with those differences. We will estimate treatment effects for time to event variables via hazard ratios using Wald scores from Cox proportional hazard regression models. Unless stated otherwise, all statistical tests will be assessed using a two-sided $\alpha = 0.05$ alpha significance level and confidence intervals will be constructed using two-sided 95% and will be based on the normal approximation. Although multiple secondary endpoints will be evaluated we will make no adjustment for multiplicities associated with these multiple tests.

Estimation of Sample Size

The clinical hypothesis we are assessing in this trial is whether patients receiving the experimental therapy have a lower hazard of progression or death relative to patients receiving the control therapy. The statistical hypothesis is stated as:

$$H_0: \log(HR)=0$$

$$H_A: \log(HR)<0$$

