Where HR is the hazard ratio (experimental:control). For sample size calculation purposes we assume that the median PFS in the temsirolimus arm is 60% that of the pazopanib arm (3.8 months versus 6.1 months). The sample size estimate is based on a one-sided log-rank test with type one error equal to 0.10 and power of 0.80.

We will conduct an interim analysis for futility after 42 events have been observed. If the p-value used to assess futility at the interim analysis is greater than 0.4798 we will stop the trial early for futility.

Secondary Objectives

Overall survival: Overall survival is calculated from day of therapy initiation to the date of death. Patients who are lost to follow-up will be censored at date of last contact.

We will use the Kaplan-Meier estimator to estimate the OS for each group of patients (control, experimental), and the log-rank statistic will be used to test for treatment differences. We will also use the Cox proportional hazards regression model to estimate the hazard ratio (experimental:control) for OS with a 95% confidence interval.

We will also assess the response rate and report 95% confidence intervals.

Additional analyses:

Demographics

For each treatment group (control, experimental), summary statistics will be provided for age, weight, baseline disease status and prior treatments.

Toxicities

Toxicities and side effects that will be evaluated include, but are not limited to infections, renal toxicity, hepatic toxicity, and pulmonary toxicity. Methods of assessment will include monitoring blood counts, and performing laboratory tests as indicated by clinical signs and symptoms. Evidence of toxicities or adverse events will be recorded at all clinic visits. All observed toxicities and side effects will be graded (NCI CTC-AE v. 4.0) for all patients and the degree of association of each with pazopanib or temsirolimus assessed. The incidence and severity of toxicities will be compared between the two treatment arms with Fisher's exact test.

Stratification Factors

The Pocock-Simon Minimization Method will be used to randomize patients according to the following stratification factors:

- Prior nephrectomy status (yes or no)
- Prior cytokine/vaccine therapy (yes or no)

The randomization program based on this method will be developed in the Department of Biostatistics and Applied Mathematics, and the program will be available via an intranet web site of MD Anderson Cancer Center.

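### Optional improvement: the two minimisation factors are not used in any stated PFS test or model; adjusting for both would change power by roughly -0.7 to +3.5 points at equal type I error, depending on assumptions the documents do not supply

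*Combined protocol and SAP*

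**What the plan says.** Section 5.1 has patients stratified at entry by nephrectomy status and by prior cytokine/vaccine therapy. Section 13.0 (Stratification Factors) gives the mechanism: "The Pocock-Simon Minimization Method will be used to randomize patients according to the following stratification factors", followed by the same two factors.

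The analysis text does not return to them.
- **PFS test.** A one-sided log-rank test at 0.10 with 80% power appears only as the basis for the sample size.
- **Effect estimates.** "We will estimate treatment effects for time to event variables via hazard ratios using Wald scores from Cox proportional hazard regression models". No covariates are named.
- **OS.** "the log-rank statistic will be used to test for treatment differences", and "We will also use the Cox proportional hazards regression model to estimate the hazard ratio (experimental:control) for OS with a 95% confidence interval". Again no strata or covariates.
- **Interim.** Futility is judged after 42 events against a p-value of 0.4798. The test that produces this p-value, and its sidedness, are not stated, while the section's general default is two-sided.
- **Status of the stop.** "we will use stopping rules for futility to serve as guidelines for early termination", with the rules "selected in a manner such that the overall type 1 error is controlled at a one-sided 10% with 80% power".

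Nothing in the plan forbids an adjusted analysis.

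**The concern.** Minimisation balances the arms on the chosen factors, so the treatment effect estimate varies less between trials than the usual variance formula assumes. An analysis that omits prognostic balancing factors keeps the larger variance. It stays valid but runs below its nominal size and gives up some power. In a 90-patient trial aiming at 80% power, a point or two recovered from data already recorded at allocation is worth having if it is nearly free.

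The plan also leaves open whether the PFS p-value comes from a log-rank or a Cox Wald test. That gap exists with or without adjustment, and writing 'one-sided log-rank test' would close it. It is an occasion to settle the model, not an argument for adjusting.

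**Working it through.** **Inputs from the documents.** 90 patients, 1:1; median PFS 3.8 v 6.1 months; one-sided 0.10; power 0.80; interim at 42 events; boundary 0.4798 (Section 13.0). Prior nephrectomy 67% (Section 3.2.3, from the cited temsirolimus phase 3 population, used as a proxy).

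**Reproducing the design.**
- HR = 3.8/6.1 = 0.623; ln HR = -0.4733; (1.2816 + 0.8416)² = 4.508.
- Schoenfeld: 4 × 4.508/0.4733² = 80.5, so 81 events.
- Freedman: 4.508 × (1.623/0.377)² = 83.5, so 84 events, which is 2 × 42. The final event count is not stated; 84 is inferred.
- Power at 84 events without the look: Φ(0.4733 × √84/2 - 1.2816) = 81.3%.
- Joint normal calculation (correlation √(42/84)) with the futility stop followed: power 79.4%, type I error 9.4%, and 6.9% of trials stopped at HR 0.623.

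The stated design is reproduced.

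**Simulating adjustment.** Assumptions throughout: exponential times, no dropout, prognostic HRs of 1 to 2. 'Equal size' means that each final test is calibrated to type I error 0.10.

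*Set A:* 24-month accrual, 67% nephrectomy, 10% prior cytokine, minimisation probability 0.8, 84 events, power with the futility look, 100,000 trials per cell.

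| Prognostic HRs (no nephrectomy / prior cytokine) | 1/1 | 1.3/1.3 | 1.5/1.5 | 2/1.5 | 2/2 |
|---|---|---|---|---|---|
| Type I, final test alone, unadjusted log-rank % | 10.12 | 10.15 | 9.81 | 9.38 | 9.23 |
| Type I, final test alone, adjusted Wald % | 10.45 | 10.70 | 10.44 | 10.53 | 10.40 |
| Power at nominal 0.10, unadjusted % | 78.9 | 77.9 | 76.9 | 74.8 | 74.4 |
| Power at nominal 0.10, adjusted % | 78.8 | 78.3 | 78.3 | 78.3 | 78.2 |
| Power change at equal size, points | -0.5 | -0.2 | +0.5 | +1.6 | +2.1 |
| Adjusted at 0.094 minus log-rank at 0.10, points | -1.0 | -0.4 | +0.6 | +2.6 | +2.9 |

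*Set B:* 36-month accrual, no futility look, 81 or 84 events, 40,000-60,000 trials per cell. Change at equal size:
- 1/1: -0.5 to -0.7.
- 1.5/1.5: +0.8 (67%/20% prevalence) to +1.2 (50%/50%).
- 2/2: +2.2 to +2.3 (67%/10%), +2.6 to +2.7 (67%/20%), +3.2 (67%/30%, minimisation probability 0.9), +3.5 (50%/50%).
- Nephrectomy alone at HR 2: +1.7.
- Type I error at 2/2: unadjusted about 8.5-9.2%, adjusted 10.6-10.8%.

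A smaller run (12,000 trials per cell, no futility look) gave about -0.6, +0.9 and +1.8 at 1/1, 1.5/1.5 and 2/2.

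Set A treats 0.623 as the effect within factor levels. If it is the whole-population HR instead, the equal-size changes for the last four scenarios are -0.2, +0.5, +1.5 and +1.9, so the reading hardly matters.

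**Size of the adjusted test.** At critical p 0.094 the final test alone has type I error 9.81-10.04% in Set A. With the stop followed, the joint normal calculation turns these into about 9.3-9.5%. At nominal 0.10 with the stop followed, Set A gives 9.8-10.1%. Score (10.5-10.8%) and likelihood-ratio (10.4-10.7%) forms do not remove the excess seen without the stop.

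**Interim boundary.** At HR 0.623, 0.4798 stops 7.4-7.7% of trials adjusted v 7.2-8.0% unadjusted, so it can stay.

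**Four-stratum log-rank test.** At equal size it loses about 2 to 2.5 points at 1/1 (Set A -2.2; Set B -1.9 to -2.5) and gains only 0.6 to 1.25 at 2/2.

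**The case against.** The best case against acting is that the current analysis is valid, simple and errs on the safe side, while the sign of the change depends on something unknown. The documents give no prognostic HR for either factor in poor-risk disease and no prior-cytokine prevalence. Their only data on a factor conflict. Section 2.2 reports median PFS, pazopanib v placebo, of "7.4 months vs. 4.2 months for cytokine-pretreated patients" and 11.1 v 2.8 months for treatment-naive patients. Prior cytokine therapy therefore looks unfavourable on pazopanib (11.1/7.4 = 1.5) and favourable on placebo (2.8/4.2 = 0.67). That control was placebo, and Section 2.3 says the vast majority of patients in such trials "had good- or intermediate-risk disease", so the pattern is only indicative. All of this stands, and it is why the point is optional.

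It also stands that adjustment does not restore 80% power. At 0.094, Set A gives 77.3-77.9% with the futility look. The 0.094 value is tuned to assumed settings.

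A reader might infer that a log-rank test ignoring the factors is invalid after minimisation, or inflates type I error. The simulations show the reverse: it stays at about 10% or falls below. A reader might also take the gap at nominal 0.10 (3.8 points at 2/2 in Set A, up to 7.6 in Set B) as the gain. Part of that gap arises only because one test runs above 10% and the other below, so equal size is the fair comparison.

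**Conclusion.** The omission is real, and its consequence is small. Adjusting for both factors is an optional, inexpensive improvement, not the correction of an error. At equal type I error it costs about 0.5 to 0.7 points if neither factor is prognostic, gains about half a point to 1.2 points at HR 1.5 for each, and gains about 2 to 3.5 points at HR 2 for each. The upper end depends on how evenly patients split on the factors, so no single range is a bound. The results rest on assumed prognostic HRs, prevalences, minimisation probability, accrual, exponential times and an inferred 84 final events. The documents do not support a claim that the gain will occur in this population, only that it would if the factors are strongly prognostic.

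**What to change.** State in Section 13.0 that the primary PFS comparison, interim and final, is the one-sided test of treatment from a Cox model containing treatment, prior nephrectomy (yes/no) and prior cytokine/vaccine therapy (yes/no). State also that the unadjusted log-rank test is a sensitivity analysis, and that the 0.4798 rule is applied to this model's one-sided p-value.

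Then choose one way to hold the size:
- a critical p-value of about 0.094, set by simulation with the actual minimisation settings and described as keeping type I error at most about 0.10 (about 9.3-9.5% if the futility stop is followed);
- a re-randomisation p-value at 0.10; or
- nominal 0.10, if the futility stop is declared binding.

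A four-stratum log-rank test is less attractive at this sample size unless the factors modify the treatment effect. The OS Cox model may carry the same covariates for consistency; no OS gain is claimed.

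Cost: revised wording and a small simulation or re-randomisation task, with no new data, since both factors are recorded at allocation. If the factors are not prognostic, the loss is about 0.5 points at equal size, or about 1 point at 0.094 against the log-rank test at 0.10. If the team prefers no adjustment, it should still name the one-sided log-rank test for both looks.

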5.0 TREATMENT PLAN

5.1 Study Summary

Patients with advanced poor-risk clear-cell RCC who have not had any prior systemic targeted therapy will be randomized fairly in a 1:1 ratio to receive pazopanib or temsirolimus as first-line therapy. Patients will be stratified upfront by nephrectomy status (yes/no) and prior cytokine/vaccine therapy (yes/no). At the time of disease progression, patients will be offered the option of crossover to receive the agent they did not receive in the first-line.

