5.4 Evaluation During Treatment (initial treatment or crossover)

*Evaluations while on study will have a standing window of allowance equal to +/- 7 days.

Treatment evaluations will consist of the following study activities (a cycle is 4 weeks):

- Interim medical history and physical examination, including vital signs, height, current weight including recent weight loss every 4 weeks for temsirolimus patients. (May be done by local physician every other cycle for temsirolimus patients only). Interim medical history and physical examination, including vital signs, current weight including recent weight loss every 8 weeks for pazopanib patients.
- All patients will complete a follow-up Quality of Life assessment battery (see Section 7 for additional details)
- Weekly blood pressure monitoring for the first four weeks for patients receiving pazopanib, and then with each history and physical every 8 weeks. Monitoring may be performed at doctor's office or by the patient at home using an electronic blood pressure device. Blood pressure measurements performed outside of the office of the treating physician should be recorded by the patient and submitted to the treating physician during cycle one. An increase in blood pressure to > 160 systolic or > 100 diastolic should be reported to the treating physician immediately.
- Urinalysis (U/A) every 8 weeks. Patients who have urine protein ≥ 300 on U/A should have a random UPC ratio checked for pazopanib patients only.
- Patients on Pazopanib will have serum chemistry and electrolytes including total protein, albumin, alkaline phosphatase, AST, ALT, calcium, LDH, total bilirubin, BUN, creatinine, phosphorus, glucose, sodium, potassium, chloride, and carbon dioxide will be done every 2 weeks for the first 8 weeks and 8 weeks x 2, and every 16 weeks thereafter. Pazopanib patients will have CBC with platelet count and differential every 2 weeks for the first 8 weeks, every 8 weeks x 2, and every 16 weeks thereafter.

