5.6 Crossover Phase

- At progression by RECIST, if they have not suffered an adverse event that would preclude them from continuing with systemic therapy and after the applicable washout period, of 2 weeks, patients who continue to meet the eligibility criteria will begin treatment with the remaining agent.

Note:

- At the discretion of the treating physician, the patient may continue on their 1st-line agent if the treating physician believes the patient is benefitting, despite progression by RECIST.
 - Patient may start their 2nd-line therapy within 2 weeks from the last dose of the agent given in 1st-line, if felt indicated by the treating physician.
 - Patients who develop progressive disease while receiving the 1st-line agent may receive radiation therapy or undergo surgery if indicated and continue to receive treatment on protocol, as long as the 2nd-line agent is commenced within 8 weeks from discontinuation of the 1st-line agent.
- For the cross-over stage of the study, patients will repeat the schedule of assessments as provided in the study calendar and section 5.4. Cardiovascular assessments will only be repeated if more than 24 weeks from the previous exams and only for those who'll be receiving pazopanib. A MRI/CT of the brain will be performed at crossover to rule out any progression before the start of crossover therapy at the discretion of the physician.
 - Screening blood work must have been performed within the past 14 days before starting the new treatment.
 - Optional blood draws will continue the same schedule as indicated in the study calendar.

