7.0 QUALITY OF LIFE ASSESSMENT

Measuring quality of life (QOL) outcomes in cancer patients has become an important mandate for clinical trials. It is especially important to assess QOL in phase II cancer clinical trials that are likely to move into the phase III setting. The extent to which treatment impairs QOL is information the patients need when making treatment decisions.

Patients will experience somewhat different symptoms when they receive the different therapies. In order to assess the effects of these treatments, we will assess multidimensional aspects of QOL over the treatment course.

Assessment Schedule

All patients will complete a full assessment battery at baseline, prior to treatment. Patients will then complete an assessment battery every 8 weeks when they come in for their clinical evaluation (see Table 1).

Table 1: Data collection sessions for psychosocial measures

BASELINE	FOLLOW-UP (EVERY 8 WEEKS)

• FACT-G• FKSI-15• Depression (CES-D)	
• FACT-G• FKSI-15• CES-D

Instruments

Several measures used previously in our work on chronic stress and QOL will be used in the proposed study. In all cases, they have proven to be useful and sensitive measures of stress and QOL, have proven to be stable, reliable, and valid with groups of people who are and are not suffering from major depression or other psychiatric disorders.

Quality of Life

The Functional Assessment of Cancer Therapy (FACT) is a cancer-specific measure of health-related quality of life. This instrument was able to discriminate between individuals with metastatic and non-metastatic disease, as well as between patients at different stages of illness. The scale has been found to have good concurrent validity, high internal consistency (0.89), and good test re-test reliability (0.82 to 0.88). The FACT will be completed at each assessment. Kidney cancer specific QOL symptoms will be assessed with the FKSI-15 from the FACT group.

Depression:

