Data Analyses for Quality of Life Measures

Prior to inferential procedures, extensive descriptive analyses will be conducted for each of the measures obtained at each session. Descriptive statistics (e.g., means, ranges, standard deviations) will be computed, together with ninety-five percent confidence intervals for the means. Proportions of subjects falling outside normative ranges for the stress and QOL measures will also be calculated. Values for the standardized scales will be compared to normative data and patients receiving other types of cancer therapy. Graphical methods (e.g., boxplots and histograms) will be employed to more closely examine the distributions of the

measures at each time point. Change scores for the stress and QOL measures will be computed as the simple differences between the baseline measure and subsequent evaluations. Bivariate associations between the raw scores, the change scores, optimism, social support, and demographic variables will be evaluated using Pearson's product moment correlation coefficients together with scatterplots where appropriate. These procedures will allow us to thoroughly characterize the stress and QOL profiles of this patient population across the sessions.

In this study, numerous models will be constructed to analyze the data and, therefore, the results will be treated as hypothesis generating and interpreted with caution. Inferential statistics will comprise paired t-tests of the stress and QOL measures. Significant test results ($p < .05$) will be interpreted as indicating significant changes in depression and QOL associated with the treatment. The association between depression and survival and TTP will also be examined.

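### Quality-of-life change scores run from the pre-treatment baseline through questionnaires answered after crossover, so a significant change cannot be attributed to either drug

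*Combined protocol and SAP*

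**What the plan says.** Section 7.0 fixes one baseline: "All patients will complete a full assessment battery at baseline, prior to treatment". It then sets the follow-up: "Patients will then complete an assessment battery every 8 weeks when they come in for their clinical evaluation". No last questionnaire is named.

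Section 5.1 states that at progression "patients will be offered the option of crossover to receive the agent they did not receive in the first-line". Section 5.4, whose title covers both the initial and the crossover treatment, lists the questionnaires: "All patients will complete a follow-up Quality of Life assessment battery". Section 5.6 adds: "For the cross-over stage of the study, patients will repeat the schedule of assessments as provided in the study calendar and section 5.4". The calendar in Section 9.0 shows the QOL battery at screening and every 8 weeks.

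The analysis rule is in Section 13.0, under the QOL data analyses: "Change scores for the stress and QOL measures will be computed as the simple differences between the baseline measure and subsequent evaluations". The inferential method is the paired t-test, with p < .05 taken to show change in depression and QOL due to treatment. The same paragraph says that many models will be built and that the results are hypothesis generating. Section 14.1 separates the first and second stage of therapy, but only for toxicity.

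**The concern.** A change score supports a statement about a treatment only if the patient was on that treatment when the later questionnaire was completed. Here the later questionnaires can fall on the other drug. They also follow progression, which may change QOL whatever drug is given. Section 13.0 does not stop the scores at crossover, set a second baseline or split the tests by treatment period. It does not say whether the paired tests are run by arm either.

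Section 7.0 justifies collecting QOL on the ground that the two therapies are expected to produce somewhat different symptoms. A score that runs across both drugs cannot show that difference, and its p-value would be read as evidence about a single treatment. Adding a between-arm test later would not solve this, because its input scores would still be mixed.

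**Working it through.** The documents give no QOL sample size, standard deviation, completion rate or crossover rate, so there is no stated figure to reproduce. The check has two parts.

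**1. Does the text lead to mixing?**
- Collection: Sections 5.4 and 5.6 together put the battery into the crossover phase.
- Definition: Section 13.0 takes all evaluations after baseline, without restriction.
- Correction elsewhere: none found. Section 14.1 covers toxicity only.

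No sentence says outright that crossover questionnaires enter the change scores. It follows from these provisions read together.

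**2. How large could it be?**

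Inputs from the documents:
- Median PFS 3.8 months (temsirolimus) and 6.1 months (pazopanib), the design values in Section 13.0.
- Median overall survival 10.9 months, the temsirolimus result cited in Section 2.3.
- Imaging every 8 weeks (Section 5.4) and a 2-week washout after progression (Section 5.2).

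Assumptions:
- PFS and survival are exponential, and the 10.9-month median holds in both arms.
- A fraction c = 0.4 to 0.8 of surviving progressors cross over and answer; the rest do not answer.
- Someone answering on the second drug at week 24 had progressed by about week 16. A progression first seen on the week-24 scan would usually be found before the second drug starts.

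Share of survivors who have progressed by time t: p = 1 - 0.5^(t/median PFS) / 0.5^(t/10.9).

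At week 16, t = 112/30.4375 = 3.68 months:
- Survival: 0.5^(3.68/10.9) = 0.791.
- Temsirolimus: 0.5^(3.68/3.8) = 0.511, so p = 1 - 0.511/0.791 = 0.354.
- Pazopanib: 0.5^(3.68/6.1) = 0.658, so p = 1 - 0.658/0.791 = 0.168.

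Share of answers from the second drug: c·p / (c·p + 1 - p).

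| Randomised to | c = 0.4 | c = 0.8 |
|---|---|---|
| Temsirolimus | 0.142/(0.142 + 0.646) = 18% | 0.283/(0.283 + 0.646) = 30% |
| Pazopanib | 0.067/(0.067 + 0.832) = 7% | 0.134/(0.134 + 0.832) = 14% |

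Sensitivity to the delay: if every switch happened at once, p at week 24 (5.52 months) would be 0.481 and 0.241.
- Temsirolimus: 0.192/(0.192 + 0.519) = 27% to 0.385/(0.385 + 0.519) = 43%.
- Pazopanib: 0.096/(0.096 + 0.759) = 11% to 0.193/(0.193 + 0.759) = 20%.
- With c = 0.25 to 0.75 and no delay, the shares are 19-41% and 7-19%.

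Week 8: p is 0.196 and 0.088. So even with every surviving progressor crossing over without delay, the shares could not exceed about 20% and 9%. With the first scan at week 8 and a washout after it, few patients would be on the second drug by then.

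**The case against.** The strongest reply is that Section 13.0 never assigns a change score to a drug or an arm and specifies no between-arm QOL contrast. Its descriptive aim is to characterise this patient population across sessions, and following patients through crossover is a legitimate whole-course summary. This stands in part. A reader might infer that the rule pulls the two arms together, but the plan contains no comparison in which that could happen. Post-crossover scores also carry the effect of progression, so the direction cannot be predicted. What remains is that the plan attributes a significant change to the treatment, and after crossover there is no single treatment.

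A second reply is that repeating the calendar at crossover could include repeating the screening battery, which would give a new baseline. That is a possible reading of collection, but Section 13.0 never uses a second baseline.

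Third, a reader might apply the PFS medians directly and conclude that 28-43% and 17-29% of week-24 answers come from the other drug. With the same week-16 cut, those figures need 49% and 34% of patients to be living progressors. PFS events include deaths, so that overstates the share. Section 5.6 limits it further: patients must still meet eligibility, may stay on the first agent beyond RECIST progression, and may start the second up to 8 weeks after stopping the first. Nor do the documents establish that mixing is heavier in the arm that progresses sooner. That needs similar crossover uptake and questionnaire completion in both arms, and neither rate is given.

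Finally, the endpoint is tertiary and the results are labelled hypothesis generating. This limits the severity. The caution is tied to the number of models, however, and does not tell the reader that a score may belong to a different drug.

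**Conclusion.** The concern holds as a gap in the analysis rule. Applied as written, Section 13.0 mixes first-drug, second-drug and post-progression answers in one change score and offers a significant result as evidence about treatment.

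The estimate of roughly 18-30% of week-24 answers (temsirolimus first) and 7-14% (pazopanib first) is only illustrative. It depends on exponential curves, a common 10.9-month median survival, the delay before second-drug answers, and an assumed 40-80% of surviving progressors crossing over and answering.

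Severity is minor. The data to be collected should allow the periods to be separated, and the PFS, overall survival and response analyses do not use these scores.

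**What to change.** In the QOL paragraphs of Section 13.0:

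- Compute and test first-line change by randomised arm, using only questionnaires completed before the first dose of the second agent. Cutting at that dose, not at RECIST progression, fits Section 5.6, which allows the first agent to continue past progression.
- Analyse later questionnaires separately by drug received, with the last pre-crossover score as baseline.
- If an all-visits summary is wanted, keep it as a secondary description that is not attributed to one drug.

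The cost is wording only, with no new questionnaires. The date of the first second-agent dose must be available in the analysis data. The documents do not list it as a data item, but the pazopanib pill diary (Section 5.2) and the drug administration records (Section 5.4) should supply it.

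There are two drawbacks. The first-line analysis loses late questionnaires, and its remaining late scores come from patients still on their first drug, a selected group. The report should say so.
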